#### 2.1.3.2.4 *Exploratory efficacy endpoints*

The other secondary efficacy endpoints are considered exploratory and include:

- Rate of acute IPF exacerbations at 52 weeks in the mITT population
- Rate of respiratory hospitalizations and rate of non-elective hospitalizations at 52 weeks in the mITT population
- Change from baseline in 6-MWT distance at 52 weeks in the mITT population
- Change from baseline in HRCT lung interstitial score at 52 weeks in the mITT population
- Change from baseline in the total score of the SGRQ at 52 weeks in the mITT population
- Change from baseline in the total score of the EQ-5D-5L at 52 weeks in the mITT population

#### 2.1.3.2.5 *Acute IPF exacerbations endpoint*

All acute IPF exacerbations events are recorded during the study on the AE e-CRF page. To help the investigator in diagnosing an acute IPF exacerbation, an “IPF Exacerbation Complementary” e-CRF form has to be completed.

For efficacy analysis, only acute IPF exacerbations with a confirmed diagnosis on the “IPF Exacerbation Complementary” e-CRF form and occurring from randomization to Day 375 will be considered.

In addition, the following information is recorded on this complementary form:

- Diagnosis of AE,
- Clinical evaluations
  - unexplained worsening or development of dyspnea within 30 days,
    - if no what is the symptom or finding of the patient related to this AE,
  - worsening of hypoxemia from a known baseline arterial blood gas,
  - pulmonary infection ruled out by endotracheal aspiration or broncho-alveolar lavage (BAL),
    - if no, was pulmonary infection ruled out by routine clinical practice and/or microbiological studies
  - have alternative causes (including left heart failure, P.E., acute lung injury, tec.) been excluded
- Radiology assessment
  - HRCT performed
    - If yes, did it show new ground-glass abnormality and/or consolidation consistent with a UIP pattern

- Final diagnosis
  - Based on response provided, do you believe that the patient experienced an acute IPF exacerbation
- Management
  - Was corrective treatment/therapy used

#### *2.1.3.2.6 Respiratory and non-elective hospitalizations endpoints*

All hospitalizations are recorded during the study on the “Hospitalization” e-CRF page.

The respiratory hospitalizations occurring from randomization to Day 375 will be considered will be selected from the “Hospitalization” e-CRF page using reason = “Respiratory”.

The non-elective hospitalizations occurring from randomization to Day 375 will be considered will be selected using the Yes response to the “nonelective hospitalization” item on the “Hospitalization” e-CRF page.

#### *2.1.3.2.7 Change from baseline in 6-MWT distance endpoint*

The total distance covered by the patient over a 6 minute walk is planned to be measured at Visit 2 (Day 1) predose, Visit 6 (Week 12), Visit 7 (Week 24), Visit 8 (Week 36), Visit 9/EOT (Week 52), Visit 10/EOS (Week 64), and reported in meters on the “6 Minute Walk Test - 6MWT” e-CRF page.

Additional information to assess quality will be reported using the “6 Minute Walk Test - 6MWT” e-CRF page:

- the completion of the 6 minute walk test (If No, what was the time patient walked? (in seconds)),
- the need of any pauses or breaks (if Yes, duration of pause (in seconds) and reason for pause were recorded).

Of note: If during visits 6, 7, 8, 9 and 10, oxygen saturation is less than 88% under ambient air at rest, the patient should perform 6-MWT under 4L oxygen.

#### *2.1.3.2.8 Change from baseline in HRCT lung interstitial score endpoint*

The HRCT lung interstitial score is adjudicated in a blinded manner, and planned to be assessed at screening (unless already done within 1 year prior to screening) and Visit 9/EOT (Week 52) (in Germany, second assessment at 52 weeks based on Investigator’s judgment).

The Total Fibrosing ILD, Reticular, Ground Glass Opacification (GGO), Honeycomb and Emphysema scores are recorded in six lobar regions (namely: RUL, LUL, RML, LML, RLL and LLL).

For each lobar region:

- The sum of the 3 patterns (Reticular, GGO and Honeycomb) should be 100%
- The Total Fibrosing ILD and the Emphysema scores ranges from 0 to 100%

The score of interest will be the Total Fibrosing ILD score averaged on the 6 lobar regions.

Each pattern score and Emphysema total score are the mean of values observed in the 6 lobar regions.

In case of image quality issue, a value NE will be recorded. For any other issue, a value NA will be recorded. A score will be calculated only if at least 4 of the 6 lobar regions are filled in (other than NE or NA).

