#### 2.4.4.2.3.4 Change from baseline in HRCT lung interstitial score endpoint

The absolute change from baseline in HRCT lung interstitial score endpoint will be analyzed on the mITT population. Assessments at week 52 will be used regardless of whether the patient has previously discontinued treatment. No imputation will be performed for the week 52 missing values of HRCT lung interstitial scores. Only patients having both the baseline and week 52 Total Fibrosing ILD score assessments available will be considered in the analysis.

The change from baseline at 52 weeks in Total Fibrosing ILD score will be analyzed using an ANCOVA model with fixed effect for treatment arm, adjusted on baseline Total Fibrosing ILD score, Emphysema total score at baseline, and the stratification factor (with/without Background Therapy) covariates, with a stratification factor-by-treatment interaction will be performed. The SAR156597 qw arm will be tested versus Placebo at a two-sided type I error level of 10% first and if significant, will the SAR156597 q2w arm be tested versus Placebo at a two-sided type I error level of 10% using the appropriate contrast. The adjusted Least Square Means (LSMeans) and their 90% CIs will be assessed for each treatment arm.

Descriptive statistics for values and changes from baseline in Total Fibrosing ILD score will be described over time by treatment arm and by background therapy status. The mean (SD) Total Fibrosing ILD score values and the mean (SD) absolute change from baseline in Total Fibrosing

ILD score over time will be graphically represented by treatment arm and by background therapy status.

The representation of LSmeans (SE) over time will be displayed by treatment arm and background therapy status for the Total Fibrosing ILD score.

In addition, descriptive statistics for values and changes from baseline in pattern score and the Emphysema total score will be described over time by treatment arm and by background therapy status. The mean (SD) scores values and the mean (SD) absolute change from baseline in scores over time will be graphically represented by treatment arm and by background therapy status.

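### The HRCT change score does not require the same lung regions on both scans, so unreadable regions can add artefactual change, mainly noise, to this exploratory endpoint

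*SAP*

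**What the plan says.** SAP 2.1.3.2.8 divides the lung into six parts: "scores are recorded in six lobar regions (namely: RUL, LUL, RML, LML, RLL and LLL". The endpoint is a mean over them: "The score of interest will be the Total Fibrosing ILD score averaged on the 6 lobar regions". For the companion scores it says: "Each pattern score and Emphysema total score are the mean of values observed in the 6 lobar regions".

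The same section expects some regions to be unreadable: "In case of image quality issue, a value NE will be recorded. For any other issue, a value NA will be recorded". It sets a minimum for each score: "A score will be calculated only if at least 4 of the 6 lobar regions are filled in (other than NE or NA".

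The analysis section, SAP 2.4.4.2.3.4, admits patients on this condition: "Only patients having both the baseline and week 52 Total Fibrosing ILD score assessments available will be considered in the analysis". It also says: "No imputation will be performed for the week 52 missing values of HRCT lung interstitial scores". Change is then analysed by ANCOVA, adjusted for baseline Total Fibrosing ILD score, baseline Emphysema score and background therapy. The qw arm is tested against placebo at two-sided 10%, followed by q2w if qw is significant.

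No text in these two sections, in the missing-data conventions (SAP 2.5.3), in SAP Appendix B or in protocol 9.1.4.3 ties the Week 52 regions to the baseline regions. None of them fills in an unreadable region or plans a sensitivity analysis on complete or common regions.

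**The concern.** The four-region minimum applies to a score, and the analysis needs only two scores. A patient may therefore have six regions averaged at baseline and a different four or five averaged at Week 52. If the regions that drop out carry more or less fibrosis than the rest, the difference of the two means mixes real change with a change in which regions were counted.

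Protocol 9.5 relies on HRCT scoring to measure the extent of fibrosis and the drug's effect on it, so imprecision here blurs the plan's most direct reading of that effect. The two scans also need not be of similar quality: protocol 9.1.4.3 accepts a baseline scan taken up to a year before screening.

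**Working it through.** The plan states no sample size, SD, expected effect or unreadable-region rate for HRCT, so there is no figure of its own to reproduce. The check covers what the rule permits and how large the effect could be under stated assumptions.

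**Inputs from the SAP (2.1.3.2.8 and 2.4.4.2.3.4).** Six regions, each scored from 0 to 100%. At least four are needed for a score. Both scores must exist. Nothing is imputed.

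**How many region sets are allowed.** Per scan: C(6,4) + C(6,5) + C(6,6) = 15 + 6 + 1 = 22. Baseline and Week 52 pairs: 22 × 22 = 484, of which 484 - 22 = 462 use different sets. Two scans may share as few as two regions.

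**One patient, assumed extents.** Four upper and middle regions at 15%, two lower regions at 45%, true change +5 in every region.

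- Baseline mean, six regions: (4×15 + 2×45)/6 = 25.
- Week 52, all six readable: (4×20 + 2×50)/6 = 30; change +5.0.
- Week 52, one lower region lost: (4×20 + 50)/5 = 26; change +1.0.
- Week 52, both lower regions lost: (4×20)/4 = 20; change -5.0.
- Week 52, one upper or middle region lost: (3×20 + 2×50)/5 = 32; change +7.0.

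With a milder 10%/30% split, the baseline is (4×10 + 2×30)/6 = 16.7. Losing one lower region gives (4×15 + 35)/5 - 16.7 = +2.3, and losing both gives 15 - 16.7 = -1.7. If all regions have the same extent, the artefact is zero.

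**Across patients, assumed random missingness.** This simulation assumes no true change and the same regional profile in every patient, with regions unreadable independently of each other, of scan and of arm. Profiles are upper/middle/lower extents in percent.

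| Assumed unreadable rate per region | Evaluable patients with different region sets | SD of artefact, 10/20/40 | SD of artefact, 15/20/30 | Evaluable patients with at least 4 common regions |
|---|---|---|---|---|
| 2% | 21% | 1.2 | 0.6 | 99.9% |
| 5% | 45% | 2.0 | 1.0 | 99.0% |
| 10% | 69% | 2.7 | 1.4 | 94% |

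The mean artefact is about zero in every row, so under these conditions the effect is noise and not a shift. Without a documented SD for HRCT change, the noise cannot be converted into lost power.

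**Does scoring common regions help?** When no region changes, its artefact is exactly zero. A harder case is worsening in the lower regions only: start at 15/45 and add 15 to each lower region, for a six-region change of (2×15)/6 = +5.

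- One lower region lost. Plan: (4×15 + 60)/5 - 25 = -1.0. Common regions: (4×15 + 60)/5 - (4×15 + 45)/5 = 24 - 21 = +3.0.
- Both lower regions lost. Plan: 15 - 25 = -10.0. Common regions: 15 - 15 = 0.

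Common-region scoring still understates change here, but it is closer to +5 in both cases.

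**The case against.** The strongest reply is that the size of the problem is unknown. No passage describes how fibrosis is spread across regions or how often a region is unreadable. If poor quality usually spoils a whole scan, the patient fails the four-region rule, is excluded, and contributes no artefact. The sign reversal above needs both lower regions, and only those, to be lost. All of this stands, so the figures are illustrations and not estimates.

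It can also be said that averaging each scan over its own readable regions is an inference, because the SAP does not state the denominator for Total Fibrosing ILD when regions are missing. That is true, but it is the natural reading, and the companion scores are explicitly means of observed values. Dividing by six regardless would be worse. In the 15/45 example it gives 130/6 - 25 = -3.3 with one lower region lost and 80/6 - 25 = -11.7 with both.

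A reader might infer that the rule biases the treatment comparison, because sicker patients give poorer scans. The documents do not support that. Scoring is blinded and allocation randomised. Readability that depends on illness but is alike across arms adds noise or shifts all arms together. Bias between arms needs readability to differ by arm, and nothing in the documents shows that it does.

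There is also a fair objection to one form of remedy. Recomputing the baseline covariate from regions readable at Week 52 would make it depend on a post-randomisation event. The fix avoids this.

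**Conclusion.** The gap is real. The stated rules allow change to be taken between averages over different regions, and no other text prevents it. How much this matters rests on two things the documents do not give: how uneven fibrosis is across regions, and how often single regions are unreadable. Under the assumed gradients and rates, individual patients can be off by several points in either direction, and the artefact SD is 0.6 to 2.7 points.

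The expected consequence is lost precision in an exploratory endpoint. HRCT is tested at two-sided 10%, outside the 5% hierarchy for the primary and disease-progression endpoints (SAP 2.4.4.3), so those conclusions are not affected. A reader should not conclude that the plan produces false improvement in the active arms.

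**What to change.** In SAP 2.1.3.2.8:

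- Define the change in Total Fibrosing ILD score as the mean Week 52 minus baseline difference over regions scored (neither NE nor NA) on both scans, calculated only when at least four such common regions exist. Use the same rule for the descriptive changes in Reticular, GGO, Honeycomb and Emphysema scores.
- State the denominator for a single-scan score: the readable regions on that scan.
- Keep the baseline scores reported under SAP 2.1.1, and the two baseline covariates in the ANCOVA, as baseline-scan scores from all readable regions, so that they do not depend on Week 52.

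In SAP 2.4.4.2.3.4, add a sensitivity analysis in patients with all six regions scored on both scans. A table of NE and NA counts by region, scan and arm would also show whether readability differs by arm.

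The cost is a few lines of SAP text and minor programming on region-level scores already recorded. Patients with fewer than four common regions drop out: about 0.1%, 1% and 6% of otherwise evaluable patients at the assumed 2%, 5% and 10% rates (100 minus the last column of the table). Change in a region unreadable on either scan is not captured, and for some patients the reported change will no longer equal the difference between their two reported scan scores, which a table footnote should say.

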#### *2.1.3.2.9 Change from baseline in total score of St George Respiratory Questionnaire (SGRQ) endpoint*

Impact of IPF on quality of life health status will be assessed using SGRQ planned to be measured at Visit 2 (Day 1) predose, Visit 6 (Week 12), Visit 7 (Week 24), Visit 8 (Week 36), Visit 9/EOT (Week 52) and Visit 10/EOS (Week 64).

Three component scores are calculated for the SGRQ:

- **Symptoms:** effect of respiratory symptoms, their frequency and severity
- **Activity:** activities that cause or are limited by breathlessness
- **Impacts:** range of aspects concerned with social functioning and psychological disturbances resulting from airways disease

A **Total** score is also calculated which summarizes the impact of the disease on overall health status.

Scores are expressed as a percentage of overall impairment where 100 represents worst possible health status and 0 indicates best possible health status (1).

Data handling conventions and detailed definitions are described in [Table 5](#).

#### *2.1.3.2.10 Change from baseline in total score of EuroQol Questionnaire, 5 level system (EQ-5D-5L) endpoint*

EQ-5D is a generic measure of health status developed by the EuroQol Group in order to provide a simple, measure of health for clinical and economic appraisal. It was designed for self-completion by patients.

EQ-5D-5L is planned to be measured at Visit 2 (Day 1) predose, Visit 8 (Week 36), Visit 9/EOT (Week 52) and Visit 10/EOS (Week 64).

EQ-5D-5L is the 5-level system for the 5-dimensional format of the EQ-5D and covers the measurement of mobility, self-care, usual activities, pain/discomfort and anxiety/depression. Each dimension has 5 levels: no problems, slight problems, moderate problems, severe problems, and extreme problems. Scores on the 5 levels are used to create an index score derived from population weights. The United Kingdom population-based scoring will be used to derive an index score from -0.594 to 1.0 renamed the EQ-5D-5L total score.

In addition, the EQ-5D has a single visual analogue scale (VAS) (0-100) to evaluate perceived current health.

Of note: There should be only one response for each dimension. Missing values can be coded as '9' and ambiguous values (e.g. 2 boxes are ticked for a single dimension) should be treated as missing values (2).

Further explanations are available in [Appendix D](#).

### 2.1.4 Safety endpoints

The safety analysis will be based on:

- the reported adverse events (AEs) including serious adverse events (SAEs) and adverse events of special interest (AESIs)
- and other safety information, such as:
  - clinical laboratory data,
  - vital signs,
  - electrocardiogram ECG.

#### *Observation period*

The observation period will be divided as follows:

- The **pre-treatment** period is defined as the time from the signed informed consent date up to the first administration of IMP.
- The **treatment-emergent adverse event (TEAE)** period is defined as the time from the first administration of the IMP to the last administration of the IMP + 84 days. It will include both **treatment** and **residual treatment** periods:
  - The **treatment** period is defined as the time from the first administration of the IMP to the last administration of the IMP + 7 days
  - The **residual treatment** period is defined as the time from the last administration of the IMP + 8 days to the last administration of the IMP + 84 days.
- The **post-treatment** period is defined as the period of time starting the day after the end of the TEAE period (ie, 85 days after the day of last dose of double-blind IMP injection).

The on-study observation period is defined as the time from the first administration of IMP until the end of the study (defined as last protocol planned visit (end of study visit) or the resolution/stabilization of all SAEs and adverse events of special interest (AESIs)).

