Archive blood samples (protein and mRNA biomarkers) ^v		X								X							X			
Blood DNA for genomics ^w		X																		

- a Randomization/baseline Visit is defined as Day 1. Visit windows for subsequent visits are +/- 2 days.
- b All assessments at Visit 2 (Day 1) are to be conducted predose with the exception of the assessment of local tolerability of SC injections.
- c Supplementary calls may be made to supply IMPs kits directly to patient's home.
- d Study treatment to be administered once a week, either at the site level or at home by a nurse.
- e Complete physical examinations will include skin, nasal cavities, eyes, ears, respiratory, cardiovascular, gastrointestinal, neurological, lymphatic and musculoskeletal systems. [REDACTED] Nail beds (periungual areas) should be examined for "splinter lesions" and digital tuft for tuft purpura or ischemia. Gynecological and urogenital examinations will not be done in this study unless for cause.
- f Vital signs, including blood pressure (mmHg), heart rate (beats per minute) and body weight (kg) will be measured at screening, baseline and every subsequent visit. Height (cm) will be measured at screening (Visit 1) only. BMI will be calculated automatically at all visits.

- g* Hematology: Hemoglobin, hematocrit, red blood cell count, erythrocyte sedimentation rate (ESR), white blood cell count with differential and platelet count. Biochemistry: Fasting glucose, blood urea nitrogen, creatinine, sodium, potassium, chloride, bicarbonate, calcium, phosphorous, total protein, albumin, total bilirubin, alkaline phosphatase, ALT, AST, CPK, hs CRP. Urinalysis (dipstick) to include: specific gravity, pH, glucose, ketones, blood, protein, nitrate, leukocyte esterase, urobilinogen and bilirubin. If any parameter on the dipstick is abnormal, a urine sample should be sent to the central laboratory for testing. If positive for proteins, microscopic analysis is performed by central laboratory.
- h* Serology testing includes hepatitis B surface antigen, hepatitis B surface antibody, hepatitis B core antibody, and hepatitis C antibodies.
- i* [REDACTED]
- j* Tuberculosis screen: history and QuantiFERON-TB Gold test. If result of QuantiFERON-TB Gold test is indeterminate, the test should be repeated.

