11.4.3 Analyses of safety data

The summary of safety results will be presented by treatment group on the basis of the safety population.

All safety analyses will be performed on the safety population using the following common rules:

- The baseline value is defined generally as the last available value before randomization.
- For quantitative safety parameters based on central laboratory/reading measurements, descriptive statistics will be used to summarize results and change from baseline values by visit and treatment group.
- The analysis of the safety variables will be essentially descriptive and no hypothesis testing is planned.

The following definitions will be applied to laboratory parameters, vital signs and ECG:

- The potentially clinically significant abnormality (PCSA) values are defined as abnormal values considered medically important by the Sponsor according to predefined criteria/thresholds based on literature review and defined by the Sponsor for clinical laboratory tests, vital signs, and ECG.

- PCSA criteria will determine which patients had at least 1 PCSA during the TEAE period, taking into account all evaluations performed during the TEAE period, including unscheduled or repeated evaluations. The number of all such patients will be the numerator for the on-treatment PCSA percentage.

The TEAE observation period is defined as the time from first dose of IMP up to 12 weeks after the last dose of IMP.

Analysis of the adverse event data

Treatment-emergent AEs, treatment-emergent SAEs, TEAEs leading to treatment discontinuation and treatment-emergent AESIs will be summarized for each treatment group based on MedDRA coding of verbatim terms reported by investigators.

Analysis of TEAE

Treatment emergent adverse event incidence tables will be presented by system organ class (SOC) (sorted by internationally agreed order), high-level group term (HLGT), high level term (HLT) and preferred term (PT), sorted in alphabetical order for each treatment group, the number (n) and percentage (%) of patients experiencing at least one TEAE. Multiple occurrences of the same event in the same patient will be counted only once in the tables within a treatment phase. The denominator for computation of percentages is the safety population within each treatment group.

Analysis of all treatment-emergent SAEs

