### 2.1.6 Immunogenicity variables

All measurements (scheduled or unscheduled) will be assigned to analysis windows defined in Table 7, in order to provide an assessment of the ADA parameter at each time point planned to be collected as per protocol.

Anti-SAR156597 antibodies (ADA) samples are planned to be collected at approximately the same times as the PK samples, namely: Visit 2 (Day 1), Visit 4 (Week 4), Visit 6 (Week 12), Visit 7 (Week 24), Visit 8 (Week 36), Visit 9 (EOT visit at Week 52) and Visit 10 (EOS visit at Week 64).

ADA positive patients are patients with at least 1 treatment-induced or treatment-boosted ADA positive sample during the TEAE period, where

- Treatment induced ADAs: ADAs developed de novo (seroconversion) following administration of the biotherapeutic (i.e., formation of ADAs any time after the initial drug administration in a subject without pre-existing ADAs). If the baseline ADA sample is missing or non-reportable and at least one reportable ADA sample is available during the treatment (including follow-up period) the baseline sample will be considered as “negative” for data analysis. This is considered being a conservative approach for ADA assessment.
- Treatment boosted ADA: Pre-existing ADAs that were boosted to a higher level following administration of biotherapeutic (i.e., any time after the initial drug administration) the ADA titer is significantly higher than the baseline titer. A low serial dilution schema (2-fold or 3 fold) should be applied during titration. A difference in titer values of two titer

steps between an on treatment or follow-up sample and its baseline sample is considered significant. For examples, at least a 4-fold increase in titers for 2-fold serial dilution schema (or 9-fold increase in titers for 3- fold serial dilution schema). If no titer could be determined for a positive sample, the titer will be reported as the MRD of the assay.

The rest will be classified as ADA negative or inconclusive patients.

The following variables will be described:

- ADA response (Positive, Negative or inconclusive). For ADA positive:
  - Titer levels
  - Neutralizing status (Positive or inconclusive)
- Pre-existing positive ADA defined as patients with positive ADA response at baseline with less than a specific increase (depending on titer calculation, e.g. 4-fold increase in titer for 2-fold serial dilution schema, 9-fold increase in titer for 3-fold serial dilution schema) in the post-baseline period

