In case of a complete treatment period (with a Yes answer to “Did the subject complete treatment period per protocol?” recorded on the End of Treatment” eCRF page), the patient will be censored at the completion date.

The incidence of premature study discontinuation will be presented graphically by treatment arm, background therapy status on randomized patients, using Kaplan-Meier method. The time-to-event variable is defined as: event date – randomization date + 1 day, where an event could be:

- a study discontinuation without a 12-week follow-up.
- a study discontinuation with a 12-week follow-up but occurring before week 52.
- a death occurring before week 52 (without previous EOS) recorded on the “Death” eCRF page.

In case of a complete study period (i.e. with at least 12 weeks of follow-up ending after week 52), the patient will be censored at the completion date.

A patient is considered lost to follow-up at the end of the study if he/she is not assessed at the last protocol planned visit and if the time from the last successful contact (from the vital patient status case report form) to the last protocol planned visit is greater than 2 days, unless died before.

Patient with insufficient follow-up will be described.

A patient is considered with insufficient follow-up or without follow-up at the end of the study in the following cases:

- If the patient is not assessed at the scheduled follow-up visit, or any post-treatment visit, unless patient died before;
- If the follow-up visit is less than 12 weeks after the last double-blind IMP injection.

All critical or major quantitative deviations potentially impacting efficacy, randomization and drug-dispensing irregularities, and other important deviations will be summarized in tables giving numbers and percentages of deviations by treatment arm. These deviations are listed in the data review and surveillance plan. All critical or major qualitative deviations will be described.

Additionally, the analysis populations for safety, efficacy, pharmacokinetics, immunology and biomarkers will be summarized in a table by number of patients on the randomized population.

- Efficacy population: modified intent-to-treat (mITT) population
- Safety population
- Pharmacokinetics population
- Anti-Drug Antibody population
- Pharmacodynamics biomarker populations: Biomarker TARC population, Biomarker ICAM1 population, Biomarker HE4 population, Biomarker Periostin population, Biomarker IL-6 population.

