### ***General common rules***

All safety analyses will be performed on the safety population as defined in [Section 2.3.2](#), unless otherwise specified, using the following common rules:

- Safety data in patients who do not belong to the safety population (eg, exposed but not randomized) will be listed separately. The baseline value is defined in [Section 2.1.4](#).
- The potentially clinically significant abnormality (PCSA) values are defined as abnormal values considered medically important by the Sponsor according to predefined criteria/thresholds based on literature review and defined by the Sponsor for clinical laboratory tests, vital signs, and ECG (PCSA version dated March 2014 [[Appendix A](#)]).
- PCSA criteria will determine which patients had at least 1 PCSA during the TEAE period, taking into account all evaluations performed during the TEAE period, including unscheduled or repeated evaluations. The number of all such patients will be the numerator for the on-treatment PCSA percentage.
- The treatment-emergent PCSA denominator by arm for a given parameter will be based on the number of patients assessed for that given parameter in the TEAE period by treatment arm on the safety population.
- For quantitative safety parameters based on central laboratory/reading measurements, descriptive statistics will be used to summarize results and change from baseline values by time point and treatment arm. Summaries will include the endpoint baseline value, the last on-treatment value and change from baseline, the worst on-treatment value and change from baseline. The last on-treatment value is commonly defined as the last value collected during the treatment period (see [Section 2.1.4](#)). The worst on-treatment value is defined as the nadir and /or the peak post-baseline during the treatment period according to the direction (minimum or maximum) of the abnormality as defined in the PCSA list.
- All measurements (scheduled or unscheduled) will be re-allocated as given in [Section 2.5.4](#) and re-allocated visits measurements will be included in the by-time point summary.
- The analysis of the safety variables will be essentially descriptive and no systematic testing is planned. Relative risks versus placebo and their 95% CIs may be provided, if relevant.

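### The 84-day post-dose cut-offs have no visit tolerance, so compliant completers can be labelled insufficiently followed, or have in-window Visit 10 results left out of treatment-emergent PCSA counts

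*SAP*

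**What the plan says.** SAP 2.1.4 (Observation period) states that the treatment-emergent "period is defined as the time from the first administration of the IMP to the last administration of the IMP + 84 days". The post-treatment period starts the next day ("ie, 85 days after the day of last dose of double-blind IMP injection"). Protocol 11.4.3 uses the same length: "time from first dose of IMP up to 12 weeks after the last dose of IMP".

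SAP 2.2 lists the cases in which a patient has insufficient or no follow-up. One of them is: "If the follow-up visit is less than 12 weeks after the last double-blind IMP injection". In the same section, the curve for premature study discontinuation censors a patient as complete only if follow-up lasted at least 12 weeks and ended after Week 52.

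The protocol synopsis and footnote a of the flow chart (Protocol 1.2) give the visit tolerance: "Visit windows for subsequent visits are +/- 2 days". Protocol 10.1 counts visit dates from the first injection. Protocol 8.1 allows 2 days either side for each weekly dose, also counted from the first administration.

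The treatment-emergent period feeds two further definitions:

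- SAP 2.4.5 (General common rules): "PCSA criteria will determine which patients had at least 1 PCSA during the TEAE period".
- SAP 2.1.6: "ADA positive patients are patients with at least 1 treatment-induced or treatment-boosted ADA positive sample during the TEAE period". The same section lets a treatment-emergent ADA response run up to the follow-up visit.

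**The concern.** Both cut-offs sit on the planned day of Visit 10, with no slack on either side. The protocol gives the visit and the dose slack in both directions, so keeping to the schedule does not protect a patient from either cut-off.

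A visit slightly early makes a fully compliant completer look under-followed. That patient also misses the 12-week condition for being censored as complete, and SAP 2.2 does not say how such a patient enters the discontinuation curve. A visit slightly late puts that day's laboratory, vital-sign and ECG results after the treatment-emergent period. A PCSA first seen there is not counted, while the patient stays in the denominator because of earlier assessments in the period. In both cases the day of the appointment decides the classification.

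The missing tolerance looks like an oversight, because the SAP applies a 2-day allowance elsewhere: in the lost-to-follow-up rule in SAP 2.2, in the dosing-compliance rule in SAP 2.4.3.2, and in the Week 64 PK and ADA window of Days 447 to 451 in SAP Table 7.

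**Working it through.** **Inputs**

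- Week 52 target: Day 365; Week 64 target: Day 449 (SAP Table 6).
- Last planned dose: Visit 9, Week 52 (protocol synopsis).
- Tolerance: 2 days either side for visits (Protocol 1.2 and 10.1) and for doses (Protocol 8.1), both counted from the first injection.
- Cut-offs: last dose + 84 days (SAP 2.1.4) and less than 12 weeks (SAP 2.2).

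**The plan's own figure**

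12 × 7 = 84 and 449 − 365 = 84. The planned gap equals both cut-offs exactly.

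**Dose on Day 365, Visit 10 anywhere in its window**

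| Visit 10 (study day) | Days since last dose | SAP 2.2 | SAP 2.1.4 |
|---|---|---|---|
| 447 | 82 | insufficient | inside period |
| 448 | 83 | insufficient | inside period |
| 449 | 84 | sufficient | inside period |
| 450 | 85 | sufficient | post-treatment |
| 451 | 86 | sufficient | post-treatment |

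**Dose also varying over Days 363 to 367**

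The shortest gap is 447 − 367 = 80 days and the longest is 451 − 363 = 88 days. The 5 × 5 = 25 combinations of dose day and visit day split as follows:

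- under 84 days: 1 + 2 + 3 + 4 = 10
- exactly 84 days: 5
- over 84 days: 4 + 3 + 2 + 1 = 10

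**Which outputs use the cut-offs**

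- Affected by an early visit: the insufficient-follow-up description and the completeness condition (SAP 2.2).
- Affected by a late visit: PCSA incidence for laboratory, vital-sign and ECG data (SAP 2.4.5.3, 2.4.5.4 and 2.4.5.5), which counts only the treatment-emergent period.
- Not affected by a late visit: Week 64 by-time-point tables (SAP Table 6 takes everything after Day 406), listings with PCSA flags, and the liver displays, which use any post-baseline visit (SAP 2.4.5.3, Drug-induced liver injury).
- ADA: SAP 2.4.7 takes all samples whatever their timing relative to injections. The patient counts it lists are of pre-existing and treatment-emergent ADA, and the latter runs up to the follow-up visit.

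**Check of the tolerances in the fix**

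84 − 2 − 2 = 80 and 84 + 2 + 2 = 88. No compliant combination falls below 80 or above 88 days.

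**The case against.** The strongest reply is that no rule asks a visit to meet both cut-offs. The treatment-emergent period dates events and measurements, and the insufficient-follow-up flag only describes patients; it removes nobody from an analysis population. Protocol and SAP agree on 12 weeks. Protocol 4.2.2 supports that length with a half-life of about 11 to 15 days, so 84 days is at least 84 / 15 = 5.6 half-lives. A fixed end counted from the last dose is a legitimate choice. All of this stands, and it limits the point to labelling and counting.

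A reader might infer more, and the documents do not support it:

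- **That 40% of completers are misclassified on each side.** The 10/5/10 split counts calendar combinations. It becomes a share of patients only if dates are assumed to spread evenly, and even then it is not a share of changed results. A late Visit 10 alters a PCSA count only if the patient had no such PCSA earlier in the period.
- **That the washout ADA sample is lost.** SAP 2.4.7 and the Week 64 window in SAP Table 7 keep it. What remains is the mismatch between two definitions within SAP 2.1.6.
- **That late safety data disappear.** They stay in the outputs listed above. An adverse event with onset by day 84 but reported later is still treatment-emergent, and post-treatment events have their own overview or listing.

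The reply does not rescue the follow-up label. A rule that calls a patient who kept every window insufficiently followed is wrong on the plan's own terms.

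**Conclusion.** The point holds in a limited form. Followed literally, SAP 2.2 labels compliant completers seen before day 84 as insufficiently followed and leaves their status in the discontinuation curve unclear. SAP 2.1.4 excludes in-window Visit 10 laboratory, vital-sign and ECG results after day 84 from PCSA incidence. The two ADA definitions in SAP 2.1.6 do not match.

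The size is known only as a range of days: 82 to 86 after a Day 365 dose, and 80 to 88 if both windows are used. How many patients would change PCSA status cannot be derived, because it depends on actual dates and on abnormalities seen first at Visit 10. The safety analysis is descriptive, the rule is the same in all arms, and the primary efficacy analysis is untouched. Severity is minor.

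The calculation applies to patients whose last dose is in the Week 52 window. With a last dose one week earlier, on Day 358, an in-window Visit 10 falls 89 to 93 days later, after the period under either limit.

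**What to change.** 1. **SAP 2.2.** Build the tolerance into insufficient follow-up and into the 12-week completeness condition, for example by using fewer than 80 days after the last injection in place of less than 12 weeks.
2. **SAP 2.4.5, PCSA counting.** Include evaluations up to last IMP + 88 days for every patient, as a hard limit. Do not use the later of + 84 days and Visit 10. Under Protocol 10.3.4, patients who stop treatment are still followed to scheduled completion, so a last dose at Week 24 with Visit 10 at Week 64 would give (64 − 24) × 7 = 280 days. Record the departure from Protocol 11.4.3 in SAP Table 1, which already lists departures made without an amendment.
3. **SAP 2.1.6.** Align the ADA-positive definition with the treatment-emergent one, up to the follow-up visit. Protocol 11.4.3 also ties ADA positivity to the treatment-emergent period, so note this in Table 1 too.

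While editing, reconcile SAP 2.1.5, which puts the Week 64 sample 14 weeks after the last injection, with the 12 weeks used elsewhere.

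The cost is a few lines of text before database lock. The downside is that up to 88 − 84 = 4 more days of measurements count as treatment-emergent, equally in all arms.
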